3.1.4.3 Hyperglycaemia

In the event of suspected persistent hyperglycaemia in a subject based on either symptoms of hyperglycaemia (eg, thirst, polyuria, blurred vision), capillary blood glucose readings (eg, 3 readings > 260 mg/dL [14.4 mmol/L] within one week) or CGM readings (eg, $> 30\%$ of readings above 260 mg/dL [14.4 mmol/L]), the investigator should perform additional fasting blood glucose levels as necessary to further investigate. If 2 or more laboratory plasma fasting glucose levels of > 260 mg/dL [14.4 mmol/L] more than 3 days apart are detected, the investigator should consider rescue therapy following discussion with the medical monitor.

3.2 Study Design and Dose Rationale

3.2.1 Dose Rationale

PK information collected in previous single and multiple dose clinical studies (Studies D5670C00001 and D5670C00002) suggest that MEDI0382 has a linear profile in the dose range 5 to 300 μ g with a half-life of approximately 8 to 13 hours, which allows minimal accumulation after repeat daily administration and achievement of steady state between 4 and 7 days. Moreover, the absorption profile in the low-dose range tested suggests that doses lower than 100 μ g may have a different bioavailability to doses greater than 100 μ g.

Based on PK/pharmacodynamics (PD) modelling conducted using available clinical data and from a literature review of GLP-1 and glucagon modulators, the maximal clinically efficacious dose for glucose control of MEDI0382 was predicted to be in the range of 200 to 300 μ g/day; in addition early clinical data from a prior single-ascending-dose study (Study D5670C00001) identified potentially efficacious doses in a range lower than 100 μ g. However, there is no information available on efficacy with repeat dosing at dose levels below 100 μ g. The initial dose for Cohorts 1 and 2 of this study is therefore proposed to be 50 μ g and the maximum dose to be administered in this study will not exceed 300 μ g/day. As

described above, the principle of dose up-titration to improve tolerability with higher doses is well established with short-acting GLP-1 analogues ([Victoza, 2014](#)).

The study is designed to provide efficacy information on glucose control and weight loss at 300 µg administered daily for 28 days to allow comparison with previous clinical data collected at 200 µg at a similar administration duration. It will also explore a prolonged dose titration schedule for repeated doses of MEDI0382 to characterise the safety/tolerability profile and PK/PD profile of MEDI0382 at a relevant pharmacological range to facilitate rational design of future studies. Moreover, it is designed to establish the efficacy of repeated dosing of 50 µg MEDI0382 on glucose control.

[REDACTED]

[REDACTED]

[REDACTED]

[REDACTED]

[REDACTED]

[REDACTED]	[REDACTED]	[REDACTED]	[REDACTED]	[REDACTED]
[REDACTED]	[REDACTED]	[REDACTED]	[REDACTED]	[REDACTED]
[REDACTED]	[REDACTED]	[REDACTED]	[REDACTED]	[REDACTED]
[REDACTED]	[REDACTED]	[REDACTED]	[REDACTED]	[REDACTED]
[REDACTED]	[REDACTED]	[REDACTED]	[REDACTED]	[REDACTED]
[REDACTED]	[REDACTED]	[REDACTED]	[REDACTED]	[REDACTED]
[REDACTED]	[REDACTED]	[REDACTED]	[REDACTED]	[REDACTED]
[REDACTED]	[REDACTED]	[REDACTED]	[REDACTED]	[REDACTED]
[REDACTED]	[REDACTED]	[REDACTED]	[REDACTED]	[REDACTED]
[REDACTED]	[REDACTED]	[REDACTED]	[REDACTED]	[REDACTED]

[REDACTED]

3.2.2 Rationale for Study Population

3.2.2.1 Recruitment of Subjects with T2DM and a Body Mass Index 27 to 40 kg/m²

MEDI0382 is a GLP-1 and glucagon receptor co-agonist which promotes glucose lowering and weight loss and is targeted at subjects with T2DM.

Male and female subjects with T2DM who are overweight or obese are likely to benefit most from losing weight. While subjects with a body mass index (BMI) > 40 kg/m² may be offered bariatric surgery, those with a BMI in the range of 27 to 40 kg/m² rely upon conservative or medical management for weight reduction. The entry criteria with respect to T2DM and BMI of 27 to 40 kg/m² both maximise recruitment potential and provide efficacy, safety, and tolerability data in the likely intended clinical population. There is no requirement for a given number of subjects in each gender to be enrolled.

3.2.2.2 Selection of Subjects with Stable HbA1c in the Range of 6.5% to 8.5% (Inclusive) on Metformin

The study population to be recruited is similar to that studied in the prior study (Study D5670C00002) with respect to HbA1c and existing diabetes treatment to enable benchmarking of results between the 2 studies, as subjects with a later stage of T2DM or who have failed multiple oral therapies may have a different glycaemic response to MEDI0382.

3.2.3 Rationale for Endpoints

3.2.3.1 Primary Endpoints

Coprimary endpoints of glucose AUC and weight loss are required to evaluate the efficacy of the 300 µg dose level over a longer duration of dosing than has been studied before at this dose level.

3.2.3.2 Secondary Endpoints

Additional Measures of Glucose Lowering and Weight Loss

In order to better characterise the glucose-lowering efficacy of MEDI0382 up to 300 µg across 49 days of dosing, additional markers of glucose control including HbA1c and fasting glucose level will be measured, alongside exploratory measures of glucose control generated by CGM. Absolute change in weight will also be measured and the proportion of subjects achieving clinically significant weight loss (> 5% of body weight) will be recorded.

In evaluating the 50 µg dose of MEDI0382, this study will determine if repeat administration of 50 µg is more effective than placebo with respect to glucose lowering at 7 days through measurement of glucose AUC during a standardised MMTT. Results from the prior multiple-ascending-dose study (Study D5670C00002) of MEDI0382 on glucose AUC reduction have shown a reduction of 41.8% after 7 days at 100 µg, 36.7% after 11 days at 150 µg following up-titration from 100 µg, and 39.6% after 15 days at 200 µg following up-titration from 100 µg and 150 µg. Results from this previous study will be used as a benchmark to further evaluate the results.

Safety and Tolerability

In prior studies (Study D5670C00002), 300 µg of MEDI0382 has been administered to 23 obese and overweight subjects with T2DM for 7 days after 2 up-titration steps, and was shown to have an acceptable tolerability and safety profile over this period of dosing. During treatment, there was no significant increase in systolic or diastolic BP, but a significant increase in heart rate of 6.6 beats per minute (90% CI 4.1, 9.1) was recorded after 7 days of dosing (Cohorts 5 and 6 pooled data; n = 19). In the cohorts that received MEDI0382 up-titrated to 300 µg, nausea and vomiting were observed in a maximum of 41.7% (Cohort 6) and 27.3% (Cohort 5) of subjects, respectively. Safety and tolerability with greater exposure at the 300 µg dose level will be measured with safety laboratory tests, ABPM recording of heart rate and BP and other vital signs, and recording of AEs.

Pharmacokinetic Profile and Immunogenicity

Plasma concentrations of MEDI0382 at 50 and 300 µg will be used to evaluate the PK profile (C_{max} , time to maximum concentration [T_{max}], AUC_{tau} , and $C_{min}[R_0]$ [accumulation ratio]). In addition, C_{trough} at other dose levels will be evaluated to establish steady state achievement.

Anti-drug antibodies (ADA) incidence rate and titre will be tabulated for each treatment to monitor immunogenicity. Tiered analyses will be performed to include screening, confirmatory and titre assay components; samples confirmed positive for ADA will be tested and analysed for antibody titre and reported and may be utilised for further characterisation of the ADA response.

3.2.3.3 Exploratory Endpoints

GLP-1 analogues are established to cause increased GI side-effects which are most pronounced in the early phases of treatment (Meier, 2012). The mechanisms underlying these symptoms are multifactorial and related to PK and effects on [REDACTED] and vomiting centers of the brain (area postrema) (Orskov et al, 1996). An added dimension of complexity here is that tolerance to the effects of GLP-1 receptor agonism on [REDACTED] may develop with short-term treatment (Nauck et al, 2011). In attempts to improve GI tolerability in this drug class, both dose up-titration (Victoza, 2014) and lengthening of titration intervals from between 1 to 4 weeks have been utilised (Exenatide, 2016). In a prior Phase 1/2 study (Study D5670C00002), subjects dosed with MEDI0382 titrated in 4-day intervals from 100 µg up to 200 µg across 41 days reported mild to moderate nausea (13/25, 52%) and vomiting (8/25, 32%); however, the number of nausea and vomiting events diminished in frequency with dose up-titration (n = 19 at 100 µg, n = 10 at 150 µg, and n = 11 at 200 µg) and in most cases, events were noted to occur within 3 days of a dose up-titration step. In Cohorts 5 and 6 of Study D5670C00002, a comparison of different dose up-titration steps was made: 100 µg → 150 µg → 200 µg → 300 µg (Cohort 5; n = 11) versus 100 µg → 200 µg → 300 µg (Cohort 6; n = 12) with 5-day up-titration steps in between. The percentage of subjects reporting nausea was lower with an intermediate 150 µg dose up-titration step between 100 and 200 µg (27% vs 42%); however, the percentage of subjects with vomiting was in fact higher in this group (27% vs 8%). These results and the prior clinical experience with GLP-1 analogues imply that further modulation of the titration schedule may help to minimise GI side-effects experienced with MEDI0382. To investigate different titration schedules, Cohort 1 of this study will test a lower starting dose of MEDI0382 (50 µg) than has been previously tested in overweight and obese subjects with T2DM, and with longer up-titration steps (7 days). Cohort 2 will run in parallel with Cohort 1

and will test up-titration of MEDI0382 every 2 weeks in order to assess if this further minimises GI AEs.

[REDACTED]

CGM is a minimally invasive device applied to the skin in the upper arm that provides a measure of interstitial glucose levels every 15 minutes. In this study, results of CGM will be used to calculate the average glucose level over 24-hour and 7-day periods, to observe glucose excursions during different meals and at different times of the day, and to determine the percentage of time subjects have abnormally high or low blood glucose levels. To further supplement this investigation, standardised meals (in some cases as part of an MMTT) will be given in the morning and evening to view the difference in post-prandial glucose excursion at different times in the day. [REDACTED]

[REDACTED]

It is postulated that the glucagon receptor agonist component of MEDI0382 may lead to an increase in fatty acid oxidation in the liver (Keller and Shulman, 1979). Ketone bodies are the byproduct of fatty acid oxidation and may be increased if there is an up-regulation of fatty acid oxidation. Concurrent measurement of free fatty acids (FFAs) and amino acids will determine if there is increased consumption of these ketogenic substrates during treatment with MEDI0382.

[REDACTED] uric acid (Gagliardi et al, 2009) are markers of cardiovascular risk; measurements before and after MEDI0382 treatment will be interpreted in the context of change in weight and lipids to gain an early insight on the impact of MEDI0382 on cardiovascular risk.

4 MATERIALS AND METHODS

4.1 Subjects

4.1.1 Number of Subjects

Enrollment of up to 63 subjects across multiple study sites is planned, 39 subjects in Cohort 1 (26 subjects to receive MEDI0382 and 13 to receive matched placebo) and 24 subjects in Cohort 2 (18 subjects to receive MEDI0382 and 6 subjects to receive matched placebo).

4.1.2 Inclusion Criteria

Subjects must meet all of the following criteria:

1. Male and female subjects aged ≥ 18 years at screening
2. Provision of signed and dated written informed consent (██████████ nongenetic research) prior to any study specific procedures
3. BMI between 27 and 40 kg/m² (inclusive) at screening
4. HbA1c range of 6.5% to 8.5% (inclusive) at screening*
5. Diagnosed with T2DM with glucose control managed with metformin monotherapy where no significant dose change (increase or decrease ≥ 500 mg/day) has occurred in the 3 months prior to screening
6. Subjects prescribed oral dual therapy with a dipeptidyl peptidase-4 inhibitor, sulphonylurea, glitinide, or a sodium-glucose co-transporter 2 inhibitor in addition to metformin at screening may be eligible to enter the study following a 4-week washout period
7. Female subjects of childbearing potential must have a negative pregnancy test at screening and randomisation, and must not be lactating
8. Females of childbearing potential who are sexually active with a nonsterilised male partner must use at least one highly effective method of contraception (see Section 10.2 for definition of females of childbearing potential and for a description of highly effective methods of contraception) from screening and must agree to continue using such precautions through to the end of the study. It is strongly recommended for the male partner of a female subject to also use male condom plus spermicide throughout this period. Cessation of contraception after this point should be discussed with a responsible physician. Periodic abstinence, the rhythm method, and the withdrawal method are not acceptable methods of contraception.

*Note: Subjects may be retested for the HbA1c entry criterion only once.

4.1.3 Exclusion Criteria

Any of the following would exclude the subject from participation in the study:

1. History of, or any existing condition that, in the opinion of the investigator, would interfere with evaluation of the investigational product, put the subject at risk, influence the subject's ability to participate or affect the interpretation of the results of the study and/or any subject unable or unwilling to follow study procedures
2. Any subject who has received another investigational product as part of a clinical study or a GLP-1 analogue-containing preparation within the last 30 days or 5 half-lives of the drug (whichever is longer) at the time of screening
3. Any subject who has received any of the following medications within the specified timeframe prior to the start of the study (Visit 2) (see Section 4.7.2 for further details):
 - Herbal preparations or drugs licensed for control of body weight or appetite (eg, orlistat, bupropion-naltrexone, phentermine-topiramate, phentermine, lorcaserin)
 - Aspirin (acetylsalicylic acid) at a dose greater than 150 mg once daily
 - Paracetamol (acetaminophen) or paracetamol-containing preparations at a total daily dose of greater than 3000 mg
 - Ascorbic acid (vitamin C) supplements at a total daily dose of greater than 1000 mg
 - [REDACTED]
4. Concurrent participation in another study of any kind and repeat randomisation in this study is prohibited
5. Severe allergy/hypersensitivity to any of the proposed study treatments, excipients, or ingredients of standardised meals
6. Symptoms of acutely decompensated blood glucose control (eg, thirst, polyuria, weight loss), a history of type 1 diabetes mellitus or diabetic ketoacidosis, or if the subject has been treated with daily SC insulin within 90 days prior to screening
7. Significant inflammatory bowel disease, gastroparesis, or other severe disease or surgery affecting the upper GI tract (including weight-reducing surgery and procedures) which [REDACTED] could affect the interpretation of safety and tolerability data
8. Significant hepatic disease (except for non-alcoholic steatohepatitis or non-alcoholic fatty liver disease without portal hypertension or cirrhosis) and/or subjects with any of the following results at screening:
 - Aspartate transaminase (AST) $\geq 3 \times$ upper limit of normal (ULN)
 - Alanine transaminase (ALT) $\geq 3 \times$ ULN
 - Total bilirubin $\geq 2 \times$ ULN
9. Impaired renal function defined as estimated glomerular filtration rate (GFR) < 60 mL/minute/1.73 m² at screening (GFR estimated according to Modification of Diet in Renal Disease [MDRD] using the isotope dilution mass spectrometry [IDMS]-traceable MDRD Study Equation [SI units])
10. Poorly controlled hypertension defined as:
 - Systolic BP > 160 mm Hg
 - Diastolic BP ≥ 95 mm Hg

after 10 minutes of seated rest and confirmed by repeated measurement at screening. Subjects who fail BP screening criteria may be considered for 24-hour ABPM at the discretion of the investigator. Subjects who maintain a mean 24-hour systolic BP \leq 160 or diastolic BP $<$ 95 mm Hg with a preserved nocturnal dip of $>$ 15% will be considered eligible.

11. Unstable angina pectoris, myocardial infarction, transient ischemic attack or stroke within 3 months prior to screening, or subjects who have undergone percutaneous coronary intervention or a coronary artery bypass graft within the past 6 months or who are due to undergo these procedures at the time of screening
12. Severe congestive heart failure (New York Heart Association Class III or IV)
13. Basal calcitonin level $>$ 50 ng/L at screening or history/family history of medullary thyroid carcinoma or multiple endocrine neoplasia
14. Haemoglobinopathy, haemolytic anemia, or chronic anaemia (haemoglobin concentration $<$ 11.5 g/dL [115 g/L] for males, $<$ 10.5 g/dL [105 g/L] for females) at screening or any other condition known to interfere with interpretation of HbA1c measurement
15. History of neoplastic disease within 5 years prior to screening, except for adequately treated basal cell, squamous cell skin cancer, or *in situ* cervical cancer
16. Any positive results for serum hepatitis B surface antigen (HBsAg), hepatitis C antibody, and human immunodeficiency virus (HIV) antibody
17. History of substance dependence, alcohol abuse, or excessive alcohol intake (defined as an average weekly intake of $>$ 21 alcoholic drinks for men or $>$ 10 alcoholic drinks for women) within 3 years prior to screening, and/or a positive screen for drugs of abuse or alcohol at screening or on admission to the study unit. Subjects who use tricyclic antidepressants or benzodiazepines for an established clinical indication may be permitted to enter the study based upon the judgement of the investigator.
18. Involvement of any AstraZeneca, MedImmune, contract research organization, or study site employee or their close relatives
19. History of acute or chronic pancreatitis or other diseases of the pancreas

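### Exclusion criterion 10: the ABPM exemption accepts either 24-hour limit, so if either seated limit excludes, a subject can enter although ABPM confirms the limit that was failed

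*Protocol*

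**What the plan says.** Criterion 10 in Protocol section 4.1.3 begins "Poorly controlled hypertension defined as" and lists two bullets: systolic BP above 160 mm Hg, and diastolic BP of 95 mm Hg or more. Neither *and* nor *or* stands between them. The readings are taken "after 10 minutes of seated rest and confirmed by repeated measurement at screening".

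The criterion then opens a second route: "Subjects who fail BP screening criteria may be considered for 24-hour ABPM at the discretion of the investigator". The route covers "Subjects who maintain a mean 24-hour systolic BP" of at most 160, or a diastolic below 95 mm Hg; the connective is in "160 or diastolic BP". A further condition, "with a preserved nocturnal dip of" more than 15%, must also be met. Subjects who satisfy this are eligible. Nothing says that the limit met on ABPM must be the one failed when seated.

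Two nearby phrases bear on how the bullets should be read. The section opens with "Any of the following would exclude the subject from participation in the study", and the bulleted laboratory limits in criterion 8 are introduced by "and/or subjects with any of the following results at screening". Criterion 10 has no such phrase of its own.

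**The concern.** The evident purpose of ABPM here is to find out whether a raised seated reading is sustained. A rule that fits this purpose clears a subject whose 24-hour mean is below the failed limit and refuses one whose mean is not. If either seated limit excludes, the exemption as written does not do this: failing one limit can be cured by meeting the other, which may never have been in question.

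What is at stake is subject safety and consistent eligibility. A recording that confirms the hypertension can make the subject eligible, and two sites can rule differently on the same recording according to how each reads the sentence. Protocol section 4.1.4 allows no exceptions to the eligibility criteria, so the criterion needs a single meaning.

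**Working it through.** The plan gives no figure to reproduce; the check is one of logic.

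**Inputs (criterion 10).** S and D are the seated readings; S24 and D24 are the 24-hour means. A dip above 15% is taken as met throughout.

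- Exclusion, either-limit reading: S > 160 or D ≥ 95.
- Exclusion, both-limits reading: S > 160 and D ≥ 95.
- Exemption as written: S24 ≤ 160 or D24 < 95.
- Alternative 1, *and*: S24 ≤ 160 and D24 < 95.
- Alternative 2, failed limit: each limit failed when seated must be met on ABPM.

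**Worked readings (values assumed for illustration; either limit excludes).**

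| Seated | 24-hour mean | Failed when seated | As written | *and* | Failed limit |
|---|---|---|---|---|---|
| 150/100 | 145/98 | diastolic (100 ≥ 95) | admitted (145 ≤ 160) | refused (98 ≥ 95) | refused (98 ≥ 95) |
| 170/90 | 165/88 | systolic (170 > 160) | admitted (88 < 95) | refused (165 > 160) | refused (165 > 160) |
| 150/100 | 140/90 | diastolic (100 ≥ 95) | admitted | admitted | admitted |
| 170/90 | 150/96 | systolic (170 > 160) | admitted (150 ≤ 160) | refused (96 ≥ 95) | admitted (150 ≤ 160) |

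The first two rows show the fault. The third is the case ABPM is meant to clear. The fourth is the kind of case on which the two alternatives differ.

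**All pass/fail patterns, either limit excludes.** Three seated patterns fail (systolic only, diastolic only, both) and there are four ABPM patterns, so 3 × 4 = 12.

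- As written, only the ABPM pattern with both limits failed is refused: 3 × 3 = 9 admitted. In 4 of the 9, ABPM confirms a limit failed when seated: one for systolic only, one for diastolic only, two for both (1 + 1 + 2 = 4). In 6 of the 9, exactly one 24-hour mean is over its limit, so the ABPM values would themselves meet the exclusion rule (3 × 2 = 6).
- With *and*: 3 × 1 = 3 admitted, none with a failed limit confirmed.
- With the failed-limit rule: 9 − 4 = 5 admitted, none with a failed limit confirmed.

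**Both limits needed to exclude.** Only one seated pattern fails, giving 4 patterns. The exemption admits 3, and in none of these do the ABPM values meet the exclusion rule, because S24 ≤ 160 or D24 < 95 is the exact complement of S24 > 160 and D24 ≥ 95. Seated 150/100 and 170/90 would not be excluded at all; seated 170/100 with a mean of 165/98 would be excluded and not exempted. On this reading the criterion is consistent.

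These are counts of logical patterns, not of patients.

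**The case against.** The fault depends on how the bullets are read. The opening line of the section governs the numbered criteria, not the bullets within one, and the absence from criterion 10 of a phrase like that in criterion 8 can be argued either way. If both limits are needed, the exemption is sound. There is also a sensible limit-by-limit reading: ABPM retests the failed reading, so *or* may mean whichever limit was failed, and then no written limit is breached. The problem case needs an investigator to order ABPM for a high diastolic, see it still high, and admit on a systolic value that nobody doubted.

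Other controls also act. ABPM is optional, the dip must exceed 15%, and criterion 1 removes subjects who would be put at risk. Blood pressure is rechecked on Day -2 (footnote a of Tables 4.2.2-1 and 4.2.2-2). Cohort 1 wears ABPM on Day -2 and again from Day 22. Earlier data at 300 µg showed no significant rise in blood pressure (Protocol section 3.2.3.2).

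What stands is that the reach is small and the text has more than one possible meaning. But either-limit remains the natural reading: the bulleted lists in criteria 3 and 8 both work that way, and a both-limits rule would not count a confirmed 190/90 as poorly controlled. The rival readings are not written down. The controls narrow the reach without correcting the rule: the Day -2 recheck does not say how it treats a subject exempted by ABPM, the Day -2 ABPM is not stated to be an eligibility test, and Cohort 2 has no ABPM during the study. The earlier 300 µg data cover 7 days at that dose, against 28 days in Cohort 1.

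**Conclusion.** The concern holds, on the condition that either seated limit excludes. On that reading the literal exemption admits subjects whose failed limit ABPM has confirmed, such as seated 150/100 with a 24-hour mean of 145/98. In 4 of the 9 pass/fail patterns it admits, a failed limit is confirmed; under either alternative rule the count is 0. If both limits are needed to exclude, or if *or* is meant limit by limit, there is no breach, but the protocol says neither.

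This is an error in the wording of an eligibility and safety rule, and it should be corrected. The number of subjects affected cannot be derived from the documents. No power, significance level or treatment comparison changes.

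**What to change.** State both connectives. Exclude on confirmed seated systolic above 160 mm Hg *or* diastolic at or above 95 mm Hg. Exempt only if the 24-hour mean has systolic at or below 160 *and* diastolic below 95 mm Hg, with the dip above 15% kept as a further condition.

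At a minimum, require that each limit failed at screening be met on ABPM. The two rules part only where the 24-hour mean is high on the limit that was passed when seated (seated 170/90 with a mean of 150/96: refused under *and*, admitted under the minimum rule). The sponsor should choose one and write it down.

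The cost is two connectives, or one clause for the minimum rule, in a single criterion. There may be a few more screen failures, fewer under the minimum rule than under *and*.
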